PTT: Partial thromboplastin time
HIV: Human Immunodeficiency virus
HBV: Hepatitis B Virus
HCV: Hepatitis C Virus
NCI: National Cancer Institute
CTCAE: Common Terminology Criteria for Adverse Events
AE: Adverse Event
CT: Computed tomography
DLCO: Diffusion capacity of the lung for carbon monoxide
HBsAg: Hepatitis B surface antigen
HBsAb: Hepatitis B surface antibody
HBcAb: Hepatitis B core antibody
DNA: deoxyribonucleic acid
RNA: ribonucleic acid
MRI: Magnetic resonance imaging
ECG: electrocardiogram
H&E: hematoxylin and eosin
IHC: immunohistochemistry
PBMC: peripheral blood mononuclear cell
PBS: phosphate buffered saline

IND: investigational new drug

IRB: institutional review board

FDA: federal drug administration

SAE: significant adverse event

DSMC: data safety and monitoring committee

CTRMSC: Clinical trial review and monitoring scientific committee

HIPAA: Health Insurance Portability and Accountability Act

CRF: Case report form

1 STUDY SUMMARY

Title	A Phase II Pilot Trial of Hydroxychloroquine, Everolimus or the Combination for Prevention of Recurrent Breast Cancer
Short Title	CLEVER Pilot Trial
Protocol Number	IRB #826253; UPCC 24116
Methodology	
This is a randomized, controlled, open label pilot trial. A total of 60 patients will be enrolled, with 15 patients allocated to each treatment arm. Patients will be evaluated at the initiation of every cycle for adverse events, and dose reduction will be employed for toxicity. Bone marrow aspiration will be performed at the end of cycle 3, cycle 6, and if patient continued on second treatment phase, at the end of cycle 12. The initial six-month study period is designed to assess the effects of HCQ, EVE and their combination. After three months of observation, control patients will be offered HCQ/EVE investigational therapy for six cycles; thus, the control group is actually a delayed treatment group and all patients will receive treatment. Patients who continue to demonstrate positive bone marrow DTCs after six cycles will be offered the opportunity to continue on combination therapy for an additional 6 cycles. Patients will continue to be followed for recurrence events for up to 3 years after completion of treatment.

Study Duration	Active Enrollment: 3 years; Follow-up: 3 years
Study Center(s)	The University of Pennsylvania and affiliated sites
Objectives	
Primary Clinical Objective: To evaluate the feasibility of administering HCQ, EVE or the combination in patients who have completed primary therapy for breast cancer and harbor bone marrow disseminated tumor cells
 
Endpoint: $\geq 75\%$ of patients in each arm reaching the 6-month evaluation time point without grade 3 or 4 toxicity.
 
Secondary Clinical Objectives:
 
1. To determine the safety of administering HCQ + EVE in combination with adjuvant endocrine therapy
 
Endpoints Incidence of adverse events within each treatment stratum and dose level by NCI CTCAE v4 criteria.
 
2. To evaluate preliminary efficacy of HCQ, EVE or the combination in reducing or eliminating DTCs
 
Endpoint

	
 • Percent change in bone marrow DTCs at 6 and 12 months of treatment relative to baseline (pre-treatment) • Incremental benefit of an additional 6 months of therapy in patients who have DTCs after initial 6 months of therapy • Incremental benefit of combination therapy compared to single-agent therapy 
3. To estimate the risk of recurrence after treatment with HCQ, EVE or the combination
 
Endpoint
 
 • 3-year recurrence free survival (RFS) 
Translational Objectives:
 
1. To assess the utility of a novel DTC assay, DTC-Flow, as a pharmacodynamic marker in trial participants to detect DTCs and their response to study therapy, compared to DTC-IHC.
 
Endpoints:
 
 • Measurement of the number and type of DTCs by DTC-FLOW before, during and at the conclusion of study therapy • Comparison to measurement of DTCs by IHC 
2. To determine whether patient DTCs biologically reflect primary tumor and predict response to study therapy.
 
Endpoints:
 
 • WES, RNA-seq, and CNV analysis will be performed on primary breast tumors and DTCs isolated by DTC-Flow to: • Identify similarities in molecular features between primary tumors and DTCs • Define genomic markers in DTCs that predict response to HCQ, EVE or their combination; 3) Identify similarities in molecular features between DTCs, CTCs and ptDNA. 
3. To determine whether patient circulating tumor cells (CTCs) biologically reflect primary tumor, accurately identify patients with bone marrow DTCs at baseline, predict for the elimination of DTCs with therapy, and/or predict for improved clinical outcomes relative to therapy
 
Endpoints:
 
 • Associations between biological and genomic features of
--	--

[figure not shown]
	
CTCs and primary tumor
 
 • Measurement of CTCs before, during and at the conclusion of study therapy, compared to DTC and clinical outcomes. 
4. To determine whether plasma tumor DNA (ptDNA) biologically reflects primary tumor, accurately identifies patients with bone marrow DTCs, or predicts response to therapy
 
Endpoints: Concordance of mutations between ptDNA and primary tumor Measurement of ptDNA before, during and at the conclusion of study therapy, compared to DTC outcomes.


Number of Subjects
	
The target number of study participants is 60

Diagnosis and Main Inclusion Criteria
	
 • Histologically-confirmed, primary, invasive breast cancer diagnosed within 5 years of study entry. • Qualifying risk status, at diagnosis, meeting one of the following: 
 ○ Histologically positive axillary lymph nodes ○ Primary tumor that is ER/PR<10%/Her2 negative ○ Primary tumor with Breast Cancer Recurrence Score of ≥ 25 per the Genomic Health Oncotype DX breast cancer test and/or high risk MammaPrint ○ Evidence of residual disease in the breast on pathological assessment after neoadjuvant chemotherapy. • Patients must have completed all primary therapy (definitive surgery, (neo)adjuvant chemotherapy adjuvant radiation and/or Her2-directed therapy) for the index malignancy at least 4 weeks prior to study entry. All prior treatment-related toxicity must be resolved prior to study enrollment. Concurrent receipt

	
of adjuvant endocrine and bone modifying agents is allowed per standard of care guidelines.
 
 • Bone marrow aspirate after completion of therapy demonstrates detectable DTCs (via IHC) • No evidence of recurrent local or distant breast cancer by physical examination, blood tests (CBC, LFTs, Alk Phos), or symptom-directed imaging, per NCCN guidelines. • Age \geq 18 years • ECOG performance status \leq 2 • No contraindications to the study medications or uncontrolled medical illness. • Adequate bone marrow function as shown by: ANC \geq 1.5 x 10⁹/L, Platelets \geq 100 x 10⁹/L, Hb >9 g/dL • Adequate liver function as shown by: Serum bilirubin \leq 1.5 x ULN, ALT and AST \leq 2.5 x ULN, and INR \leq 1.5 • Anticoagulation is allowed if target INR \leq 1.5 on a stable dose of warfarin or on a stable dose of anticoagulant for >2 weeks at time of randomization. For patients on therapeutic anti-coagulants, medication must be clinically held peri-procedure (bone marrow aspirate) per standard clinical management. • Adequate renal function: serum creatinine \leq 2.0 x ULN or creatinine clearance (CrCl) \geq 30mL/min obtained within 28 days prior to registration. A calculated creatinine clearance by Cockcroft-Gault Formula is acceptable in lieu of a measured value. • Serum cholesterol \leq300 mg/dL OR \leq7.75 mmol/L AND triglycerides \leq 2.5 x ULN. NOTE: In case one or both of these thresholds are exceeded, a fasting lipid assessment will be ordered. If one or both of these thresholds are still exceeded in a fasting state, the patient can only be included after initiation of appropriate lipid lowering medication. • Ability to provide informed consent

Statistical Methodology
	
The primary endpoint of this pilot study is feasibility. The secondary endpoints are tolerability and the measured effect of the investigational therapy on DTCs in patients with measureable DTCs at baseline and the comparison of this effect to that in a control population. Because this is proof-of-concept, sample sizes are not sufficient to address long-term recurrence risk. Randomization is being performed to minimize uncontrolled confounding.
 
The trial endpoint “feasibility” will be defined as at least 11 of 15 patients within each treatment regimen completing 6 cycles of therapy without grade 3 or 4 toxicity. While arms may be

[figure not shown]
	
discontinued for lack of feasibility, the trial may continue enrolling to those arms that remain feasible.
 
Toxicity will be assessed using NCI CTCAE v4 criteria. Patients who drop out before completing cycle 6 for reasons other than grade 3/4 toxicity will be replaced. With 15 patients per group, an exact 95% confidence interval around the feasibility and toxicity rates will be no more than 0.52 units wide.
 
We will define “response” for each patient as a 50% or greater decrease in DTC number at each treatment time point compared to baseline. A treatment arm/regimen will be considered successful if at least 3 of 15 of patients experience this predefined response endpoint.
 
We will also estimate, within each treatment group, the % change in DTC number. While the trial is powered for feasibility, rather than detection of change in DTCs across treatment group, 15 patients per group will provide 80% power (using a two-group t-test with a two-sided alpha level of 0.05) to detect a decrease of approximately 1 standard deviation and will provide important preliminary data for designing future confirmatory trials.

--	---

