7.8 Discontinuation of Treatment

Patients who discontinue study treatment prior the final planned dose will enter the follow up phase, and complete all procedures and follow-up dictated by the protocol. Patients who choose to discontinue all study participation, including follow-up, may do so at any time without penalty, by following the procedures outlined in section 7.11. At the time of any treatment discontinuation or withdrawal, site research staff should document the reasons and conditions under which discontinuation of treatment occurred and whether the patient is willing to continue follow up or will be requesting full withdrawal from the study. Each subject has the right to discontinue study treatment or withdraw from the overall study at any time without prejudice. The investigator may discontinue any subject's participation for any reason, including adverse event or failure to comply with the protocol. Because this is a randomized pilot trial following intent-to-treat principals, patients who discontinue study treatment will be followed for study outcomes as outlined in the protocol. Reasons for withdrawal from study treatment include the following:

- Delay in treatment > 28 days due to treatment-related toxicity or major event (if due to treatment-related toxicity, patient will be taken off the treatment that is most likely to be related to the toxicity).
- Disease Recurrence: Remove patient from protocol therapy at the time progressive disease is documented.
- Extraordinary Medical Circumstances: If at any time the treating physician feels constraints of this protocol are detrimental to the patient's health remove the patient from protocol therapy.
- Patient's refusal to continue treatment: In this event, document the reason(s) for withdrawal.
- Failure to comply with protocol (as judged by the investigator such as compliance below 80%, failure to maintain appointments, etc.).

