7.9 Withdrawal from Study

Patients who choose to withdraw from study participation (including any additional treatment, follow-up, or study procedures) may do so, without penalty, by sending a request to be withdrawn from the study, in writing, to the Principal Investigator. In addition, this request should specifically address whether research samples that remain in the possession of the study staff can be used for future research per the previously signed consent form. Should the patient request withdrawal from the study, the PI and project manager should be alerted immediately, and updated with the conditions of the request.

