8.8.2 Everolimus (EVE) Dose Reduction Guidelines

Known EVE hematological toxicities will not be attributed to HCQ but will only be attributed to EVE and will result in the following EVE dose modifications, as shown in Table 11. Hematologic toxicity of unexpected severity may be attributed to HCQ (in addition to EVE at investigator discretion). Non-hematological toxicities having an attribution to EVE of possible, probable or definite will result in the following EVE dose modifications, as shown in Table 11. For EVE dosing, the patient must have an ANC $\geq 1.0 \times 10^9/L$ and platelet count $> 75 \times 10^9/L$. All non-hematological toxicity grade ≥ 3 (except for alopecia, nausea and vomiting) must have resolved to CTCAE grade ≤ 1 . If toxicity persists, treatment should be delayed by one week for up to 4 consecutive weeks. If after 4 weeks (28 days) of delay all toxicity has still not resolved, any further treatment with EVE should be stopped. HCQ may be continued after EVE has been stopped on the combination arm.

Table 10: EVE Dose Reduction Guidelines

Dose Level	Dose	Reduce to
1	10 mg daily	5 mg daily
-1	5 mg daily	5 mg every other day
-2	5 mg every other day	Discontinue EVE

If any non-hematological toxicity observed Grade ≥ 3 (except for alopecia, nausea and vomiting) and/or if platelets $< 75 \times 10^9/L$ and/or ANC $< 1 \times 10^9/L$, causing delay of two weeks of EVE then the dose should be reduced by one dose level (see Table 10). For patients who would require dose >2 dose reductions EVE will be stopped. If any non-hematological toxicity observed was CTCAE **Grade 4** (except for alopecia, nausea and vomiting) then EVE should be **stopped**.

Table 11: Criteria for dose-modification for suspected EVE toxicity and re-initiation of EVE treatment

Toxicity	Actions
Non-hematological toxicity	
Grade 2 (except pneumonitis – refer to Table 6)	If the toxicity is tolerable to the patient, maintain the same dose. If the toxicity is intolerable to patient, interrupt EVE until recovery to grade ≤ 1 . If resolution occurs ≤ 7 days reintroduce EVE at same dose. If resolution takes > 7 days or if the event returns to grade 2, then interrupt EVE until recovery to grade ≤ 1 . Then reintroduce EVE at lower dose level.

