12.2 Analysis Plan

12.2.1 Primary Endpoint

The phase II trial endpoint “feasibility” is based upon the overall safety and tolerability of the treatment arms, and will be defined as at least 11 of 15 patients within each treatment group completing 6 cycles of therapy without grade 3 or 4 toxicity. When evaluating feasibility of the combination therapy, Arm C and D may be combined for analysis, since both arms receive the same study treatment (Arm D is just a delayed start). Toxicity will be determined by NCI CTCAE v4 criteria, and categorized by system and grade. Patients who drop out before the 6-month time

point for reasons other than toxicity and not related to feasibility will be replaced. With 15 patients per group, an exact 95% confidence interval around the feasibility and toxicity rates will be no more than 0.52 units wide. Arms that are discontinued for lack of feasibility will be dropped from the trial, but others may continue, so long as they remain “feasible” by this definition.

Because this is a potentially curable patient population, we will also institute an early stopping rule, should the toxicity rates exceed those expected or acceptable in this setting. To do this, we will implement a Bayesian toxicity monitoring approach with a target protocol-defined DLT rate of 30%. We assume a $Beta(1,2)$ prior, equivalent to one DLT observed in 3 treated patients. Early termination for toxicity will be considered based on a posterior probability that the toxicity rate exceeds 30%. Early termination will be considered if DLT is observed in 2 of 3 patients (0.84 posterior probability), 3 of 6 patients (0.81), 4 of 9 patients (0.79), 5 of 12 patients (0.78), 6 of 15 patients (0.78).

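### The Study Summary and Section 12.2.1 replace different dropouts under the same 11-of-15 feasibility criterion, and the Summary rule favours a finding of feasibility

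*Protocol*

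**What the plan says.** The Summary (Statistical Methodology) calls a regimen feasible if at least 11 "of 15 patients within each treatment regimen completing 6 cycles of therapy without grade 3 or 4 toxicity". Section 12.2.1 sets the same criterion. The replacement rules attached to it differ:

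- **Summary:** "Patients who drop out before completing cycle 6 for reasons other than grade 3/4 toxicity will be replaced".
- **Section 12.2.1:** patients who drop out before the six-month point "for reasons other than toxicity and not related to feasibility will be replaced".

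Neither text defines dropping out or says whether a replaced patient leaves the denominator. Section 7.8 deals with stopping treatment, after which "patients who discontinue study treatment will be followed for study outcomes as outlined in the protocol". Section 7.9 deals separately with leaving the study: "Patients who choose to withdraw from study participation (including any additional treatment, follow-up, or study procedures) may do so".

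The endpoint itself is also worded in two ways. The Summary's Statistical Methodology, Section 2.1 and Section 12.2.1 require completion of six cycles. The endpoint under the Summary's Objectives asks only that patients reach the six-month evaluation without grade 3 or 4 toxicity. The SAP text available covers the DTC count model and does not address feasibility.

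**The concern.** Two groups of patients are handled differently: those who drop out because of toxicity below grade 3, and those who drop out for another feasibility-related reason. The Summary replaces both groups and 12.2.1 replaces neither. These are patients for whom the regimen was not workable, which is what a feasibility endpoint is meant to count.

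Such cases are foreseeable. For grade 2 non-hematological toxicity, Table 11 in Section 8.8.2 says "If the toxicity is intolerable to patient, interrupt EVE until recovery to grade" 1 or below. The same table ends EVE after any toxicity that needs an interruption of more than 28 days. In Arm B that is the end of study therapy.

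Section 12.2.1 allows an arm to be dropped for lack of feasibility. With a cut-off of 11 of 15, one patient can decide the verdict, so the analyst's choice between two current texts could decide it too.

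**Working it through.** **The plan's own figure.** The protocol says the exact 95% interval with 15 patients is at most 0.52 wide. Clopper-Pearson intervals for x = 0 to 15 have a maximum width of 0.5215, at x = 7 and x = 8. This reproduces. It presupposes a denominator of 15, and the replacement rule decides who makes up that 15.

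**Who is treated differently**

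| Reason for dropping out before completing cycle 6 | Summary | 12.2.1 |
|---|---|---|
| Grade 3/4 toxicity | not replaced | not replaced |
| Lower-grade toxicity | replaced | not replaced |
| Other feasibility-related reason | replaced | not replaced |
| Unrelated reason | replaced | replaced |

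**Direction.** Every patient in the table failed to complete six cycles and so is a failure. With c successes among n patients, removing d failures changes the rate from c/n to c/(n − d), which is never lower. A replacement can turn that place into a success or leave it a failure. This is true whether the patient stopped treatment or left the study; the definition of dropping out changes only how many patients are affected.

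**Illustration by counts.** Fifteen start, 10 complete without grade 3/4 toxicity, 4 have grade 3/4 toxicity and 1 drops out for lower-grade toxicity. Under 12.2.1 the result is 10/15, not feasible. Under the Summary that one patient is replaced; if the replacement completes cleanly, the result is 11/15, feasible. The example needs a group exactly one short.

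**Illustration by rates.** The documents give no dropout rates, so the inputs are assumptions: t is the grade 3/4 rate, d1 the share in the two disputed rows, and unrelated dropout is set to zero.

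- Success rate under 12.2.1: 1 − t − d1.
- Success rate under the Summary: (1 − t − d1)/(1 − d1).
- P(≥11 of 15) is the binomial tail at each rate.

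With t = 20%:

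| d1 | Rate, 12.2.1 | Rate, Summary | P(≥11/15), 12.2.1 | P(≥11/15), Summary | Difference |
|---|---|---|---|---|---|
| 0 | 80.0% | 80.0% | 0.84 | 0.84 | 0 |
| 2% | 78.0% | 79.6% | 0.78 | 0.83 | 0.045 |
| 5% | 75.0% | 78.9% | 0.69 | 0.81 | 0.121 |
| 10% | 70.0% | 77.8% | 0.52 | 0.77 | 0.258 |

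For example, at d1 = 5%: 1 − 0.20 − 0.05 = 0.75, and 0.75/0.95 = 0.789. Because replacing a failure cannot lower the count, the last column is also the chance that the two rules give different verdicts. For t from 10% to 25%, the rate rises by 1.5 to 1.8 points at d1 = 2%, 3.7 to 4.5 at 5%, and 7.2 to 8.9 at 10%.

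**The case against.** **The direction is not universal.** A reader might infer that the Summary rule inflates feasibility under any reading of the endpoint. The documents do not support that. Under the wording in the Summary's Objectives, a patient who stops for grade 2 toxicity but is evaluated at six months counts as a success, and Section 7.8 keeps such patients in follow-up. Replacing that patient could lower the rate. This objection stands, and the claim is limited to the completing-six-cycles criterion.

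**The windows differ.** The Summary's window ends at completion of cycle 6 and that of 12.2.1 at six months. Suppose a patient completes cycle 6 with grade 3/4 toxicity and then leaves for an unrelated reason before a later six-month evaluation. That patient could be replaced under 12.2.1 only, which reverses the direction. The case is narrow: Sections 7 and 7.2 equate the six-month treatment period and the six cycles with 24 weeks. What remains is mainly the end-of-cycle-6 marrow window, which runs to 21 days after the last dose.

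**Few patients may be affected.** The intent-to-treat language in 7.8 favours reading dropping out as leaving the study. On that reading, a patient who stops treatment but stays in follow-up is replaced under neither text. Section 8.8 also allows dose adjustment to keep patients on drug. Both points bear on size. They do not remove the conflict, because a patient who leaves the study for lower-grade toxicity is still treated differently by the two rules.

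**Toxicity in 12.2.1 might mean grade 3/4.** The word is unqualified there but follows a reference to those grades. Even so, the exclusion of feasibility-related reasons has no counterpart in the Summary.

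**Conclusion.** The conflict is explicit, concerns the primary endpoint, and should be fixed. Under the completing-six-cycles criterion, and if replaced patients leave the count, the Summary rule can only raise the feasibility rate relative to 12.2.1, apart from the narrow window case. The size cannot be taken from the documents. In the illustration it runs from nothing, when no one falls in the disputed category, to a 0.258 difference in the chance of passing at an assumed 10%.

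A reader might also infer that the trial's feasibility results are inflated. The documents do not show this: they do not say which rule was applied or how many patients it affected. Confidence is high for the textual conflict and for the direction within its stated limits, but not for any particular magnitude.

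**What to change.** 1. Replace the Summary sentence with the reason rule of 12.2.1, for example: *A patient who drops out before finishing six cycles of assigned therapy is replaced only if the cause is neither toxicity of any grade nor otherwise related to feasibility. Any other such patient stays in the denominator as a failure.* State in both places that toxicity here is not limited to grade 3/4, and whether dropping out includes stopping treatment.
2. Use the completing-six-cycles wording in the Summary's Objectives and Statistical Methodology and in Sections 2.1 and 12.2.1. For Arm D, count from the start of assigned therapy, after the 12 weeks of observation.
3. List replaced patients by arm and reason.
4. Report feasibility descriptively among all patients who started therapy, with an exact 95% interval and no added threshold.
5. If the primary analysis is already done, report the result under both rules. The SAP's past tense suggests that at least the DTC analysis is complete.

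The cost is a text change and possibly a slightly less favourable feasibility rate. The reasons are already to be collected: Section 7.8 says "site research staff should document the reasons and conditions under which discontinuation of treatment occurred". How refusal, non-compliance and recurrence are classified is for the sponsor to decide and state. Section 12.2.1 also says that "Arm C and D may be combined for analysis, since both arms receive the same study treatment"; the threshold for a pooled group larger than 15 is a separate issue. No dose or clinical rule changes.
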